Outcome Variables and Assessments	
Performance
 
 • Change in IOP from medicated baseline to 3 years after XEN 45 Gel Stent implantation • Change in IOP from medicated baseline to 4 years after XEN 45 Gel Stent implantation • Study pre-defined IOP outcomes achieved while staying on the same number or fewer IOP-lowering medications and without clinical hypotony: 20% reduction from medicated baseline, IOP below 12 mmHg, below 13 mmHg, ..., up to IOP below 18 mmHg • Change in the number of topical IOP-lowering medications from medicated baseline to 3 years after XEN 45 Gel Stent implantation • Change in the number of topical IOP-lowering medications from medicated baseline to 4 years after XEN 45 Gel Stent implantation • Qualified or complete success 3 years after XEN 45 Gel Stent implantation • Qualified or complete success 4 years after XEN 45 Gel Stent implantation

	
Safety
 
 Adverse events of special interest (AESIs) as defined below in the Section "Data Collection Procedures"

Study Procedures
	
Patients' medical charts will be extracted until the study target population has been reached. Site personnel will be required to complete a screening log for patients treated with XEN 45 Gel Stent on or after 1 January 2014 until 31 December 2014 to identify eligible patients. End date can be up to 1 October 2015 if the target number of eyes for the primary analysis has not been reached. For each eye selected, retrospective data will be extracted from existing medical records from XEN 45 Gel Stent implantation until 1 October 2018 or until the date on which the patient received a SSI for glaucoma, whichever occurs first. The study will not impose any separate patient visits at the site. In case key data are not available within the charts at the site, site personnel will be asked to liaise with the patients' treating ophthalmologist to request data to be made available for investigators for data entry.
 
When both eyes from the same patient meet eligibility criteria, each eye will be included in the study database with a unique identifier, and eyes will be paired in the electronic data capture system.

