
Statistical Methods
	
Analysis Populations
 
Data will be presented for all eyes selected and meeting the selection criteria, i.e. Analysis Population. Additional groups may be also examined, as deemed appropriate (e.g. eyes that did or did not undergo phacoemulsification).
 
Primary Objective
 
Change in IOP from medicated baseline and change in the number of topical IOP-lowering medications compared to baseline will be summarized descriptively at Year 3 after XEN 45 Gel Stent implantation in eyes from the Analysis Population with at least 3 years of follow-up data and were not treated with Diamox on the day when decision was taken to implant XEN 45 Gel Stent.
 
Secondary Objectives
 
Change in IOP and Number of Topical IOP-Lowering Medications at 4 Years after XEN 45 Gel Stent Implantation
 
Change in IOP from medicated baseline and change in the number of topical IOP-lowering medications compared to baseline will be summarized descriptively at Year 4 after XEN 45 Gel Stent implantation in eyes from the Analysis Population with at least 4 years of follow-up data and were not treated with Diamox on the day when decision was taken to implant XEN 45 Gel Stent.
 
Success over the Long Term of Implantation of the XEN 45 Gel Stent
 
Number and proportion of eyes achieving a 20% reduction in IOP from medicated baseline, and number and proportion of eyes with an IOP <18 mmHg, IOP <17 mmHg, ..., down to IOP<12 mmHg will be described at all data collection time-points in eyes from the Analysis Population that did not underwent SSI for glaucoma, did not have clinical hypotony, and were not treated with Diamox on the day when decision was taken to implant XEN 45 Gel Stent.
 
The number and proportion of eyes achieving "success" at 3 and 4 years after XEN 45 Gel Stent implantation will be summarized descriptively. Analyses will be conducted in the Analysis Population. Kaplan-Meier analyses will be conducted to analyze time from initial procedure to SSI for glaucoma.
 
Safety over the Long Term of Implantation of the XEN 45 Gel Stent
 
Surgical complications and post-operative AESIs will be summarized descriptively using frequencies and percentages. Analyses will be performed in the Analysis Population.

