14.2.5 Secondary Objectives

14.2.5.1 Change in IOP and Number of Topical IOP-Lowering Medications 4 Years after XEN 45 Gel Stent Implantation

Change in IOP from medicated baseline and change in the number of topical IOP-lowering medications compared to baseline will be summarized descriptively at Year 4 after XEN 45 Gel Stent implantation in eyes from the Analysis Population with at least 4 years of follow-up data and were not treated with Diamox on the day when decision was taken to implant XEN 45 Gel Stent.

14.2.5.2 Success over the Long Term of following implantation of the XEN 45 Gel Stent

Number and proportion of eyes achieving a 20% reduction in IOP from medicated baseline, and number and proportion of eyes with an IOP <18 mmHg, IOP <17 mmHg, ..., down to IOP <12 mmHg will be described at all time-points of interest in eyes from the Analysis Population that did not undergo SSI for glaucoma, did not have clinical hypotony, and were not treated with Diamox on the day when decision was taken to implant XEN 45 Gel Stent.

The number and proportion of eyes achieving qualified or complete success at 3 and 4 years after XEN 45 Gel Stent implantation will be summarized descriptively. Analyses will be conducted in the Analysis Population. Kaplan-Meier analyses will be conducted to analyze time from initial procedure to SSI for glaucoma.

14.2.5.3 Safety over the long term following implantation of the XEN 45 Gel Stent

Surgical complications and post-operative AESIs will be summarized descriptively using frequencies and percentages. Analyses will be performed in the Analysis Population.

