1.5. Outcome Variables

Performance outcomes:

- Change in IOP from medicated baseline to 3 years after XEN 45 Gel Stent implantation
- Change in IOP from medicated baseline to 4 years after XEN 45 Gel Stent implantation
- Study pre-defined IOP outcomes achieved while staying on the same number or fewer topical IOP-lowering medications and without clinical hypotony: 20% reduction from medicated baseline, as well as IOP below 12 mmHg and through to IOP below 18 mmHg
- Change in the number of topical IOP-lowering medications from medicated baseline to 3 years after XEN 45 Gel Stent implantation
- Change in the number of topical IOP-lowering medications from medicated baseline to 4 years after XEN 45 Gel Stent implantation
- Qualified or complete success 3 years after XEN 45 Gel Stent implantation
- Qualified or complete success 4 years after XEN 45 Gel Stent implantation

Safety outcomes:

- Adverse events of special interest (AESIs), as defined in Section 1.8 below.

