 - Persistent corneal decompensation / edema (>30 days)
 - Mild corneal decompensation / edema

[figure not shown]

-
- Moderate corneal decompensation / edema
 - Severe corneal decompensation / edema
 - Cyclodialysis
 - Endophthalmitis
 - Hyphema
 - ≥ 2 mm in height (layered) at any time; present or arising > 30 days postoperatively
 - Persistent hypotony: IOP < 6 mmHg, present at two consecutive visits postoperatively > 30 days apart
 - Clinical hypotony: vision reduction (2 lines or more) related to macular changes consistent with hypotony maculopathy (macular folds), optic disc edema, and/or serious choroidal detachments because of low IOP
 - Implant blockage in the anterior chamber
 - Implant exposure or extrusion
 - Implant fracture
 - Implant migration
 - Implant repositioning requiring surgical intervention
 - Implant touching iris
 - Implant touching cornea
 - Iridodialysis
 - Iritis (requiring treatment after the postoperative medication taper)
 - Macular edema
 - Ptosis
 - Retinal detachment
 - Suture abscess or other local infection
 - Vitreous hemorrhage
 - Any other adverse event that leads to permanent visual impairment or requires surgical or medical intervention to prevent permanent visual impairment

2. Sample Size

A sample size of 150 patient eyes was selected, as it is anticipated that this will allow for the inclusion of a minimum of 60 independent study eyes have at least 3 years of follow-up data without a SSI for glaucoma after the initial implant with XEN 45 Gel Stent. Based on the Allergan study MS-001, for month 36 the 95% confidence interval (CI) of the projected mean IOP reduction afforded by a sample of 60 study eyes is -7.2 to -4.0 mmHg. That is, the half-length of the interval is 1.6 mmHg, which provides a reasonable precision for the estimate of the projected mean reduction in IOP.

3. Data Handling

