These will be compared to baseline and will be summarised descriptively at months 12, 24, 36 and 48 after XEN 45 Gel Stent implantation in eyes from the Effectiveness Population. Analyses will only include those with available data at each of the time points of interest and those who were not treated with Diamox on the day when decision was taken to implant XEN 45 Gel Stent.

A paired t-test will be applied for statistical analysis in comparing the difference between post baseline to baseline values. The assumptions of the test are as follows:

- No significant outliers in the differences between time points (which can be tested by a scatter plot of the data)
- The distribution of the differences in the dependent variable between the two time points should approximately follow a normal distribution (which can be tested through the Shapiro-Wilk test)
- The dependent variable is measured on a continuous scale

If the assumptions of the t-test are heavily violated then the non-parametric analogue (Wilcoxon Signed-Rank test) should be used to test the difference between time points.

4.4.1. Success over the long term of following implantation of the XEN 45 Gel Stent

Number and proportion of eyes achieving a 20% reduction in IOP from medicated baseline, and number and proportion of eyes with an IOP between 6 and 18 mmHg, IOP between 6 and 17 mmHg, ..., down to IOP between 6 and 12 mmHg will be described by the time-windows described in Section 4.1 in eyes from the Effectiveness Population that did not undergo SSI for glaucoma, and were not treated with Diamox on the day when decision was taken to implant XEN 45 Gel Stent.

The number and proportion of eyes achieving qualified or complete success at each time point of interest (i.e. 12, 24, 36, 48 and >51 months) after XEN 45 Gel Stent implantation will be summarised descriptively. Analyses will be conducted in the Effectiveness Population.

The time from XEN 45 Gel Stent implantation to SSI for glaucoma will be described using Kaplan Meier curves.

4.5. Safety over the long term following implantation of the XEN 45 Gel Stent

Surgical complications and post-operative AESIs will be summarised descriptively using frequencies and percentages.

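### SAP 4.4.1 counts the seven mmHg threshold outcomes without the medication and clinical-hypotony conditions that define them, and adds a 6 mmHg floor with unstated end points

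*SAP*

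**What the plan says.** **Definition.** SAP 1.5 lists "Study pre-defined IOP outcomes achieved while staying on the same number or fewer topical IOP-lowering medications and without clinical hypotony": a 20% reduction, "as well as IOP below 12 mmHg and through to IOP below 18 mmHg". Protocol 6.3 attaches the same two conditions to the same thresholds. The Outcome Variables part of the protocol synopsis does too, except that it leaves out the word topical: "IOP outcomes achieved while staying on the same number or fewer IOP-lowering medications and without clinical hypotony".

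**Protocol analysis.** Section 14.2.5.2 uses strict inequalities, below 18 down to below 12 mmHg with no floor, in eyes that "did not undergo SSI for glaucoma, did not have clinical hypotony, and were not treated with Diamox" at baseline. The Statistical Methods part of the synopsis says the same. Neither mentions the medication condition.

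**SAP analysis.** Section 4.4.1 reports the "number and proportion of eyes with an IOP between 6 and 18 mmHg", then between 6 and 17, down to between 6 and 12. The eyes are those in the "Effectiveness Population that did not undergo SSI for glaucoma, and were not treated with Diamox" at baseline.

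**Where a 6 mmHg value appears elsewhere.** SAP 1.8 has it in one adverse-event definition: "Persistent hypotony: IOP < 6 mmHg, present at two consecutive visits postoperatively > 30 days apart". Clinical hypotony is a separate entry there. It is defined by loss of two or more lines of vision with macular, disc or choroidal signs, and has no pressure value.

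**The concern.** The SAP defines the outcomes one way in section 1.5 and analyses them another way in section 4.4.1. There are three differences.

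1. **Medication.** An eye that reaches the target pressure on more drops than at baseline fails the definition but counts in the analysis.
2. **Clinical hypotony.** The protocol's analysis sections exclude these eyes. The SAP keeps the SSI and Diamox restrictions and drops this one.
3. **Boundary.** Below k has become between 6 and k, with no statement on whether 6 or k counts. Two programmers could produce different tables from the same sentence.

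The stake is whether the seven reported proportions can be presented as the pre-defined performance outcomes. No other analysis in the text supplied reports them as defined. The stand-alone 20% reduction count in 4.4.1 has the same two omissions, but qualified success (SAP 1.4) keeps both conditions and largely covers it. The mmHg thresholds have no such counterpart.

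**Working it through.** **Step 1. The texts side by side** (k = 12, 13, ..., 18, so seven thresholds)

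| Element | Definition: SAP 1.5, protocol 6.3 | Analysis: protocol 14.2.5.2, synopsis | Analysis: SAP 4.4.1 |
|---|---|---|---|
| Threshold | below k | below k | between 6 and k, end points not stated |
| No more topical medications than at baseline | required | absent | absent |
| Clinical hypotony | must be absent | eyes excluded | not mentioned |
| SSI for glaucoma | not mentioned | eyes excluded | eyes excluded |
| Diamox at baseline decision | not mentioned | eyes excluded | eyes excluded |

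**Step 2. Eyes the two SAP rules classify differently**

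- 5 mmHg, no clinical hypotony, no added drops: meets below 12, fails between 6 and 12.
- 9 mmHg with clinical hypotony: fails SAP 1.5, counts in 4.4.1.
- 11 mmHg on more drops than at baseline: fails SAP 1.5, counts in 4.4.1.
- Exactly 18 mmHg: fails below 18, counts in 4.4.1 if the upper end is included.

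**Step 3. The plan's own precision figure.** Protocol 14.1 gives a mean change of -5.6 mmHg, SD 6.32, for 60 eyes. The half-length is 1.96 × 6.32/√60 = 1.60, so the interval is -7.2 to -4.0 mmHg, as stated. It concerns the mean change, and nothing below alters it. The documents give no rate for any threshold outcome, so steps 4 to 6 rest on assumed values.

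**Step 4. Medication condition.** Assume 60 eyes, of which 42 (42/60 = 70.0%) are below 18 mmHg under SAP 4.4.1. One eye is 1/60 = 1.7 points.

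| Eyes on added drops | Of these, at target | Counted as not met | Excluded |
|---|---|---|---|
| 3 | 2 | 40/60 = 66.7% | 40/57 = 70.2% |
| 6 | 4 | 38/60 = 63.3% | 38/54 = 70.4% |
| 6 | 6 | 36/60 = 60.0% | 36/54 = 66.7% |

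If these eyes stay in the denominator as not met, leaving out the condition overstates the proportion or leaves it unchanged. If they are excluded, the difference can go either way. Protocol 5.1 cites a study of 242 eyes in which medications fell from about 3 to 0.3 at one year. That suggests few eyes above baseline but gives no share.

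**Step 5. Clinical hypotony.** Same 42/60, with h = 1, 2 or 3 affected eyes.

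- All h at target, counted as not met, (42-h)/60: 68.3%, 66.7%, 65.0%.
- All h at target, excluded, (42-h)/(60-h): 69.5%, 69.0%, 68.4%.
- None at target, excluded, 42/(60-h): 71.2%, 72.4%, 73.7%.

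**Step 6. Boundary at 18 mmHg.** Assume whole-mmHg readings from a normal distribution X with SD 4. Below 18 is P(X<17.5).

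| Reading | Formula | Mean 14 | Mean 15 | Mean 16 |
|---|---|---|---|---|
| below 18 | P(X<17.5) | 80.9% | 73.4% | 64.6% |
| 6 to 18, both included | P(5.5<X<18.5) | 85.3% (+4.4) | 80.0% (+6.6) | 73.0% (+8.4) |
| 6 included, 18 not | P(5.5<X<17.5) | 79.2% (-1.7) | 72.5% (-0.9) | 64.2% (-0.4) |
| neither included | P(6.5<X<17.5) | 77.9% (-3.0) | 71.7% (-1.7) | 63.7% (-0.9) |

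Over SD 3 to 5 and the same means, the shifts from below 18 run from +1.3 to +10.6, from -4.5 to 0.0, and from -6.7 to -0.1 points respectively.

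**The case against.** The strongest reply is that SAP 1.5 remains in force and defines the outcome, while 4.4.1 only says how it is summarised. The next sentence of 4.4.1 reports qualified and complete success without repeating their conditions. But for the thresholds, 4.4.1 lists its own eye restrictions and changes the form of the threshold, so both sections cannot be followed at once.

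Other points on that side, and what stands:

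- **The medication omission is inherited.** True: protocol 14.2.5.2 and the synopsis already lacked it. Only the dropped hypotony restriction and the 6 mmHg floor are new in the SAP. The SAP still states the condition in 1.5 and does not apply it.
- **Table shells might show otherwise.** The supplied SAP text runs from section 4.6 to section 7, so the statement that no planned table reports the outcomes as defined is limited to that text.
- **The boundary can be inferred.** Below 18 points to an excluded upper end, and a persistent-hypotony cut-off of less than 6 points to an included 6. On that reading the shift is -4.5 to 0.0 points, and the +10.6 is one corner of the assumptions. This is fair on likely size, but it remains an inference the SAP does not state.
- **The floor of 6 stands in for clinical hypotony.** It does not, because clinical hypotony has no pressure criterion.
- **The magnitudes are assumed and only the 18 mmHg row is worked.** True. They illustrate and do not predict.

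**Conclusion.** The concern holds. Followed as written, SAP 4.4.1 does not report the seven mmHg outcomes that SAP 1.5 and protocol 6.3 define: it counts eyes the definition rejects and rejects eyes it accepts. The contradiction follows from the text alone and needs no assumption.

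Its size does need assumptions. In the scenarios above, counting added-drop eyes as not met lowers an assumed 70.0% to between 66.7% and 60.0%. Handling of clinical hypotony gives 65.0% to 73.7%. The boundary reading moves the 18 mmHg row by -6.7 to +10.6 points. Only the medication effect has a fixed direction, and only if those eyes stay in the denominator.

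The outcomes are secondary and descriptive, no test or sample size rests on them, and the primary mean change is unaffected. The point should be fixed before analysis, but it does not threaten the study's main result.

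**What to change.** In SAP 4.4.1:

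- Count an eye as meeting a mmHg or 20% outcome at a time point only if its number of topical medications is no greater than at baseline and it has had no clinical hypotony. State the period over which clinical hypotony is assessed.
- Keep eyes that fail the medication condition in the denominator as not met.
- State whether eyes with clinical hypotony are counted as not met, or excluded as in protocol 14.2.5.2 and the synopsis.
- Use the pre-defined below-k thresholds and write each inequality out. If the version with a 6 mmHg floor is wanted, show it as an additional, labelled row with both end points specified.

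Then reconcile SAP 1.5 and 4.4.1 with protocol 6.3, 14.2.5.2 and both synopsis entries, including the missing word topical in the synopsis outcome list.

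The cost is SAP wording and a little programming. SAP 1.8 already has topical medication counts and clinical hypotony collected. The threshold proportions will differ slightly and will probably be lower, and the tables gain rows if the floored version is also shown.

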8.2.3 Minimum Required Dataset

Medical charts that do not include the following data will not be selected for the study. Therefore, if no data is available within the charts at the study site, before selecting the chart for inclusion in the study it must be established that certain key data from other locations will be made available for investigators for data entry.

Patient characteristics

- Age
- Gender

Intraocular Pressure

- IOP at baseline (i.e. medicated IOP) and until last visit (1 October 2018 or until the date on which the patient received a SSI for glaucoma, whichever occurs first)
- Number of topical IOP-lowering medication prescribed for the study eye at baseline and until last visit (1 October 2018 or until the date on which the patient received a SSI for glaucoma, whichever occurs first)

Secondary surgical intervention

- Date of the SSI for glaucoma, if any

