1.7. Study Population

The study population includes patients with one or both eyes with open angle glaucoma that underwent XEN 45 Gel Stent implantation.

Patients meeting the following criteria are eligible for participation in the study:

1. Eye treated with XEN 45 Gel Stent for open angle glaucoma as a standalone procedure or in combination with phacoemulsification
2. XEN 45 Gel Stent was implanted between 1 January 2014 and 1 October 2015
3. Charts contain minimum required data (age, gender, IOP at baseline until last visit, number of topical IOP-lowering medications prescribed for the study eye from baseline until last visit, date of the SSI for glaucoma if applicable)

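### The seven absolute IOP cut-offs ignore baseline IOP, so eyes already in range before surgery are counted as achieved with no IOP change required

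*SAP*

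**What the plan says.** SAP 4.4.1 carries the heading "Success over the long term of following implantation of the XEN 45 Gel Stent". Its first paragraph plans the count of eyes with a 20% reduction from medicated baseline. In the same sentence it plans the "number and proportion of eyes with an IOP between 6 and 18 mmHg, IOP between 6 and 17 mmHg", continuing "down to IOP between 6 and 12 mmHg will be described by the time-windows described in Section 4.1". The upper limits 18, 17, 16, 15, 14, 13 and 12 make seven ranges. The eyes used are those "that did not undergo SSI for glaucoma, and were not treated with Diamox on the day when decision was taken to implant". Nothing in the sentence refers to baseline IOP.

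SAP 1.5 lists these under performance outcomes as "Study pre-defined IOP outcomes achieved while staying on the same number or fewer topical IOP-lowering medications and without clinical hypotony". SAP 4.4.1 does not repeat the medication condition. Protocol 14.2.5.2 plans the same series as the "number and proportion of eyes with an IOP <18 mmHg, IOP <17 mmHg" and so on, with no lower limit, and leaves out eyes with clinical hypotony.

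On eligibility, the clinical criterion is "Eye treated with XEN 45 Gel Stent for open angle glaucoma as a standalone procedure or in combination with phacoemulsification" (SAP 1.7; also Protocol 8.2.1). The other protocol criterion is the implantation date, and Protocol 8.2.2 has no exclusion criteria. Protocol 8.2.3 requires "IOP at baseline (i.e. medicated IOP) and until last visit" to be on file, but sets no minimum value.

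SAP 1.4 defines qualified and complete success separately. Both need at least a 20% reduction from medicated baseline, and SAP 1.3.2 ties the success objective to those definitions.

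**The concern.** In a single-arm chart review, each eye's own baseline is the only comparator. The 20% criterion uses it and the seven absolute ranges do not. The reported windows start at Month 12 (SAP 4.1), and no baseline column or baseline-by-follow-up count is planned for the ranges.

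A reader shown the percentage of eyes within 6 to 18 mmHg at Month 36 cannot tell eyes brought into the range from eyes that were there before surgery. Listed as performance outcomes and placed under a heading about success, the whole percentage is likely to be read as the device's result. The mean change in IOP (SAP 4.4) does not fill the gap, because it does not show how many eyes entered each range.

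**Working it through.** **1. The plan's own figure.** The only planning figure is the confidence interval for mean IOP change (Protocol 14.1). Half-width = 1.96 × 6.32 / √60 = 1.60, so the interval is −5.6 ± 1.6, or −7.2 to −4.0 mmHg. It reproduces. It does not involve the cut-offs and is not in dispute.

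**2. The rule applied to one eye.** The rule counts an eye at upper limit c if its follow-up IOP lies between 6 and c. SAP 1.5 adds: no more topical medications than at baseline, and no clinical hypotony. Take an eye at 16 mmHg on three drops before surgery and at 16 mmHg on three drops at Month 36.

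- 6 to 18 and 6 to 17 mmHg: counted.
- At least 20% reduction: needs 0.8 × 16 = 12.8 mmHg or lower, so not met.
- Qualified and complete success: not met.

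**3. Share of eyes already in range at baseline.** The documents give no baseline mean or SD, so both are assumed, with a normal distribution. Share = Φ((c − mean)/SD) − Φ((6 − mean)/SD). For mean 20, SD 5 and c = 18: Φ(−0.4) − Φ(−2.8) = 0.345 − 0.003 = 34.2%.

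| Assumed mean | SD | 6–18 | 6–15 | 6–12 |
|---|---|---|---|---|
| 18 | 4 / 5 / 6 | 49.9 / 49.2 / 47.7% | 22.5 / 26.6 / 28.6% | 6.5 / 10.7 / 13.6% |
| 20 | 4 / 5 / 6 | 30.8 / 34.2 / 36.0% | 10.5 / 15.6 / 19.3% | 2.3 / 5.2 / 8.1% |
| 22 | 4 / 5 / 6 | 15.9 / 21.1 / 24.9% | 4.0 / 8.0 / 11.8% | 0.6 / 2.2 / 4.4% |
| 24 | 4 / 5 / 6 | 6.7 / 11.5 / 15.7% | 1.2 / 3.6 / 6.5% | 0.1 / 0.8 / 2.1% |

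**4. Share of counted eyes when the planned effect is present.** Baseline and follow-up IOP were simulated as bivariate normal (4,000,000 eyes per setting). The mean fall was the planned 5.6 mmHg, with SD 5 at both times and correlation 0.3 or 0.6. The SD of change is 5 × √(2(1 − correlation)), which gives 5.92 and 4.47; Table 4 of the protocol shows 4.92 to 6.41. Upper limit 18 mmHg:

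| Baseline mean, correlation | Counted at follow-up (all eyes) | Of counted: already below 18 | Of counted: already below 18 and less than 20% reduction |
|---|---|---|---|
| 20, 0.3 | 71.8% | 37.4% | 21.2% |
| 20, 0.6 | 71.8% | 39.8% | 18.7% |
| 22, 0.3 | 60.7% | 25.6% | 15.7% |
| 22, 0.6 | 60.7% | 29.4% | 14.9% |

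The last column is the relevant one, because the third also includes eyes that went on to fall by 20% or more. For 6 to 12 mmHg the last column becomes about 4% to 7%.

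The simulation ignores the medication condition, which can only remove eyes from the count. The numbers of eyes are therefore upper bounds within the model. At 18 mmHg they are about 9% to 15% of all eyes (for example 60.7% × 14.9% = 9.1% and 71.8% × 21.2% = 15.2%).

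**The case against.** The strongest reply is that success is a defined term. Because the section heading mentions success, a reader might infer that unchanged eyes enter the study's success rate. They do not: SAP 1.4 demands at least a 20% reduction, SAP 1.3.2 points the objective there, and SAP 4.4.1 reports qualified and complete success in a separate paragraph. Only the shared heading links them to the cut-offs. This part of the reply stands.

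A reader might also infer that an eye already below a cut-off shows no stent effect. That does not follow. Baseline IOP is medicated, and an eye held at the same IOP on fewer drops may have benefited. The documents support only the statement that no IOP change is required.

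A third tempting reading is that any eye starting below a cut-off, with zero median change, has at least an even chance of being counted. The 6 mmHg floor defeats this: in a normal model, a start of 11 mmHg against 6 to 12 gives 42% with an SD of change of 4.94 and 35% with 6.32.

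It is also true that the cut-offs are descriptive and secondary, that no test or sample size depends on them, and that the 20% count and the change analyses sit close by. This limits the weight of the point. It does not supply the missing information, since none of those results shows how many eyes moved into each range.

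**Conclusion.** The concern holds in a limited form. The seven ranges take no account of baseline IOP, nothing in eligibility keeps out eyes already in range, and no baseline proportion is planned. The follow-up percentages therefore cannot be read as eyes brought into range. Qualified success, complete success and the primary analysis are untouched.

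The size depends on a baseline distribution that the documents do not give. With the assumed means of 18 to 24 and SDs of 4 to 6 mmHg, about 7% to 50% of eyes would start within 6 to 18 mmHg. With the planned fall, baseline mean 20 to 22, SD 5 and correlation 0.3 to 0.6, about 15% to 21% of eyes counted below 18 mmHg would have started there and fallen by less than 20%. The effect can be material at the upper cut-offs and is small at the lowest. This is a worthwhile reporting correction to a descriptive table and does not invalidate the plan.

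**What to change.** In SAP 4.4.1, for each cut-off and window:

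- Report beside the follow-up proportion the proportion of the same eyes that met the cut-off at baseline. Ideally, give a baseline-by-follow-up count of eyes newly within the range, remaining within it and having left it.
- State and apply the condition of SAP 1.5 that the eye is on the same number of topical medications or fewer.
- Label these counts *IOP level attained*, and keep the word success for the SAP 1.4 definitions.

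While editing the paragraph, reconcile it with Protocol 14.2.5.2, which has no lower limit and leaves out clinical hypotony, whereas SAP 4.4.1 uses a lower limit of 6 and drops that exclusion.

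Restricting each cut-off to eyes that start at or above it, and calling only those achieved, is not recommended as the replacement. With no effect at all, mean 20 and SD 5, about 21% to 28% of eyes starting at 18 mmHg or above would still be below 18 at follow-up, through regression to the mean. Each cut-off would also have its own denominator.

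The cost is SAP wording, extra table columns and a less favourable reading of the upper cut-offs. Baseline IOP and medication number are already in the minimum required dataset, so no new data are needed.
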